8.1 Site monitoring

Before study initiation, at a site initiation visit or at an investigator's meeting, a Novartis representative will review the protocol and eCRFs with the investigators and study site personnel. During the study, Novartis employs several methods of ensuring protocol and Good Clinical Practice (GCP) compliance and the quality/integrity of the sites' data. The field monitor will visit the site to check the completeness of participant records, the accuracy of data capture / data entry, the adherence to the protocol and to Good Clinical Practice, the progress of enrollment, and to ensure that study treatment is being stored, dispensed, and accounted for according to specifications. Key study personnel must be available to assist the field monitor during these visits. Continuous remote monitoring of each site's data may be performed by a centralized Novartis Clinical Research Associate (CRA) organization.

The investigator must maintain source documents for each participant in the study, consisting of case and visit notes (hospital or clinic medical records) containing demographic and medical information, laboratory data, electrocardiograms, and the results of any other tests or assessments. All information on CRFs must be traceable to these source documents in the participant's file. The investigator must also keep the original informed consent form signed by the participant (a signed copy is given to the participant).

The investigator must give the monitor access to all relevant source documents to confirm their consistency with the data capture and/or data entry. Novartis monitoring standards require full verification for the presence of informed consent, adherence to the inclusion/exclusion criteria, documentation of SAEs, and of data that will be used for all primary variables. Additional checks of the consistency of the source data with the CRFs are performed according to the study-specific monitoring plan. No information in source documents about the identity of the participants will be disclosed.

8.2 Data collection

Designated study site personnel will enter the data required by the protocol into the Electronic Data Capture (EDC) system. Designated study site personnel will not be given access to the system until they have been trained.

Automatic validation procedures within the system check for data discrepancies during and after data entry and, by generating appropriate error messages, allow the data to be confirmed or corrected online by the designated study site personnel. The investigator must certify that the data entered into the eCRFs are complete and accurate. After database lock, the investigator will receive copies of the participant data for archiving at the investigational site.

8.3 Database management and quality control

Novartis study team will review the data entered into the eCRFs by study site personnel for completeness and accuracy and instruct the site personnel to make any required corrections or additions. Queries are sent to the investigational site using an electronic data query. Designated study site personnel are required to respond to the query and confirm or correct the data.

Concomitant medications entered into the database will be coded using the World Health Organization (WHO) Drug Reference List, which employs the Anatomic Therapeutic Chemical classification (ATC) classification system. Concomitant procedures, nondrug therapies and AEs will be coded using the Medical Dictionary for Regulatory Activities (MedDRA) terminology.

Since the study includes specific genotyping requirement as APOE4 HTs and HMs at inclusion, the results of the genotyping performed at the central laboratory will be provided to the site and be part of the source documents for the participant. Results will also be sent electronically to Novartis.

Results for brain amyloid status from CSF A β and/or amyloid PET scans will be communicated to the site to confirm eligibility of HTs. The result (elevated/non elevated) will be captured in the eCRF.

Laboratory samples will be processed centrally and the results will be sent electronically to Novartis.

ECG readings will be processed centrally and the results will be sent electronically to Novartis.

MRI images will be read centrally for safety evaluation and volumetric measures of brain regions. The results will be sent electronically to Novartis. The PET scans for AD biomarkers will be analyzed centrally and the SUVR results will be sent electronically to Novartis. The [REDACTED] CSF samples analyses results will be sent electronically to Novartis.

All clinical scales administered by the clinician or self-reported by the participant or the informant will be collected on the Virgil® tablet provided by the Cognition vendor who will also manage the database. The database will be sent electronically to Novartis with the exception of the audio recordings.

Photographs will be sent by the site to the central dermatology imaging vendor if there are treatment emergent skin AEs. Only reports (not photographs) from the central dermatologic imaging vendor will be sent electronically to Novartis.

Randomization codes and data about investigational drug dispensed to the participants and all dosage changes will be tracked using an IRT. The system will be supplied by a vendor, who will also manage the database. The database will be sent electronically to Novartis.

Each occurrence of a code break via IRT will be reported to the clinical team and monitor. The code break functionality will remain available until study shut down or upon request of Novartis.

The occurrence of relevant protocol deviations will be reported. After these actions have been completed and the database has been declared to be complete and accurate, it will be locked and the treatment codes will be unblinded and made available for data analysis. Any changes to the database after that time can only be made after written agreement by Novartis Development management.

[REDACTED]

[REDACTED]

8.4 Data Monitoring Committee (DMC)

The program-level independent DMC will review unblinded safety, and tolerability data from all participants on an ongoing basis. Regular meetings will be scheduled on an approximately semi-annual basis aligned with the DMC meetings for the study API015A2201J, starting when safety data from first participant first post-baseline visit are available. Additional *ad hoc* meetings or off-line consultation may be scheduled as needed.

The DMC will be expected to provide recommendations on any of the following:

- Enhance safety monitoring
- Suspend treatment with current dose(s) of CNP520. In this case, the sponsor may switch participants to the LDR by activating the DRM.
- Stop the trial in case of (1) unexpected safety issues, (2) futility at pre-planned one of the two IAs, or (3) outstanding efficacy at one pre-planned IA on primary efficacy endpoints.

The safety parameters to be checked will be guided by potential and theoretical compound and class risks as described in the DMC charter, applicable until treatment termination.

The DMC may also assess any potential relationship (i.e. temporal) between exposure data for CNP520 with the occurrence of a particular AE of interest at the participant level if required, or identify signs or signals of safety concerns within the study and across studies with data from the API015A2201J study Cohort II with CNP520.

The DMC will also receive all SAEs and specific reports (including CDR, RBANS, MMSE and [REDACTED], centralized safety MRI scans, and volMRI), and any other reports as described in the DMC charter or requested ad hoc at any time by the DMC. The DMC may then access the treatment codes as provided in the DMC closed reports for each participant, to assess the relationship to study medication and assess criteria for suspension or design modification as described in the DMC Charter.

The DMC will be provided with individual participant's data, as well as summaries and graphs as appropriate. The tables, listings and graphs will be prepared by independent statisticians and statistical programmers who are not otherwise involved in the planning and conduct of the trial. Content and format of the tables, listings, and graphs will be agreed with the DMC.

The DMC will be composed of recognized academic experts and will be assisted by an external independent statistician.

8.5 Progression Adjudication Committee (PAC)

A process for the adjudication of MCI/dementia diagnoses will be implemented with an external PAC managed by the Cognition vendor. Details of the diagnostic criteria are described in [Section 6.3.1](#) and a description of the PAC members, role, and function will be described in the PAC charter applicable until treatment termination. The same PAC membership and operating rules that apply for the API015A2201J study will also apply for this study as well.

The communication steps between the site and the PAC as well as key coordinating roles from the Sponsor and the Cognition vendor will also be detailed in the PAC charter.

The PAC will be provided with the available participant data to assess for possible progression and potential confounding factors for the events received for adjudication.

Adjudication data will be collected and maintained by the Cognition vendor, and transferred to Novartis at pre-defined frequency.

8.6 Disclosure Monitoring Advisory Group

The DMAG is responsible for assisting the DMC in an advisory capacity, monitoring the safety of the participants in relation to the genetic disclosure. The responsibilities of the DMAG, as also outlined in the DMAG Guidelines, are:

- Reviewing the outputs (e.g. table/figure/listing of the data from the relevant scales, adverse events (AE) and serious adverse events (SAE) reports (those deemed related to genetic and/or amyloid disclosures)) and making recommendations regarding changes or adjustments
- Providing summary reports to the DMC prior to each data review meeting summarizing any findings related to the safety monitoring of genetic and/or amyloid disclosures.

The DMAG will be composed of recognized academic experts, as described in the DMAG Guidelines.

9 Data analysis

The final analysis will occur once the overall targeted number of events for the study has been reached and all participants have completed their month 60 assessments.

In general, data will be reported by treatment arms of interest and by visit as applicable. Summaries including only baseline data, may also include a total group (All participants). In case of no DRM, treatment arms of interest are the originally defined treatment arms #1 to #3. In case of DRM, summaries will show the following treatment arms of interest: the pooled active treatment arms (Arm #1 and Arm #2) and placebo (Arm #3). In addition, summaries may also include the sub-group of participants randomized to any of the two active treatment arm after the DRM, i.e. those who started on the LDR.

In general, descriptive statistics (mean, median, standard deviation, minimum, and maximum) will be presented for continuous variables. The number and percentage of participants in each category will be presented for categorical variables.

The primary treatment arms for efficacy analysis will include the following participants based upon whether or not the DRM will be implemented.

- In the case that the DRM does not occur, the 3 treatment arms would remain the same as planned originally. The primary treatment arms are CNP520 50 mg once daily or matching placebo in a respective ratio of 1:1. The primary treatment arms include participants who received either CNP520 50 mg once daily or matching placebo. In this case, the primary active arm is Arm #1, i.e. the CNP 50 mg once daily active arm.
- In case the DRM is implemented, the same randomization ratio is maintained, 3:2 active versus placebo, namely 2:1:2 for Arm #1: Arm #2: Arm #3. The primary placebo arm (Arm #3) consists of all the participants who have been randomized to Arm #3 and received placebo regardless of DRM. The primary active arm (pooled Arm #1 and Arm #2) consists of the following participants
 1. those who received CNP520 50 mg once daily dose followed by CNP520 LDR (those who were originally randomized to Arm #1, and subsequently switch to the lower dose regimen) and
 2. those who received CNP520 15 mg once daily dose followed by CNP520 LDR (those who were originally randomized to Arm #2, and subsequently switch to the lower dose regimen) and
 3. those who received CNP520 LDR dose only (those who were randomized to active treatment arm after the DRM).

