- Cholinesterase inhibitors (ChEIs): The primary efficacy analysis will be based on an intention-to-treat principle and will neither exclude participants who started ChEIs during the study, nor exclude time points from the analysis after start of ChEIs.
- Sensitivity analysis will be carried out to investigate the role of concomitant cholinesterase therapy on the efficacy of CNP520, such as exclusion of time points from the analysis after initiation of ChEI therapy, or using this information as a stratification factor or as a time-varying covariate in the statistical models.

Other supportive analyses

In order to understand the possible difference in outcome due to the method of classifying amyloid status of HTs at baseline, a Cox PH model and MMRM model for APCC will be conducted. The models will include treatment arm as a factor, while adjusting for genotype and classification method (PET or CSF).

Sub-group analyses

Analyses similar to the primary analyses will be performed on the subset of FAS including only participants fulfilling criteria for classification for Stage 1 as defined in the draft [FDA Guidance for Industry 2018](#) Early Alzheimer's disease: Developing Drugs for Treatment

In case of DRM, analyses similar to the primary analyses will be performed on the subset of the FAS defined as participants who have been randomized after the DRM, i.e. who have been exposed to the LDR throughout the whole treatment epoch.

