17.1 Design and definitions

At randomization, participants are randomized to two active doses, CNP520 50 mg once daily (*H*) and CNP520 15 mg once daily (*L*) and a placebo control (*C*) in a 2:1:2 ratio into the 3 respective treatment arms. In case of no DRM, the CNP520 50 mg once daily dose arm is considered as the primary active arm, that is, the active arm to be used for comparison with placebo in the final primary analyses. In case of DRM, the primary active arm will be defined by pooling of the two active treatment arms (pooled P: *H* and *L*). The primary efficacy analysis furthermore consists of two endpoints (*e*), Time-To-Event (TTE) and API Preclinical Composite Cognitive Battery (APCC), designated as $e = T, A$.

A DRM may be triggered upon DMC recommendation and/or Sponsor's decision. The DRM will be a modification to lower either dose strength or dosing frequency. This lower dose regimen is referred to as the LDR.

In case that no DRM occurs, the 3 treatment arms remain the same as planned originally. The primary treatment arms are CNP520 50 mg once daily or matching placebo in a respective ratio of 1:1.

In case the DRM is implemented, the same randomization ratio is maintained. The primary active arm (pooled across all active arms) consists of the following participants:

- those who received CNP520 50 mg once daily dose followed by CNP520 LDR (those who were originally randomized to Arm #1, and subsequently switch to the lower dose regimen) and
- those who received CNP520 15 mg once daily dose followed by CNP520 LDR (those who were originally randomized to Arm #2, and subsequently switch to the lower dose regimen) and
- those who received CNP520 LDR dose only (those who were randomized to active treatment arm after the DRM).

The trial then proceeds to the final analysis and only at the final analysis, a statistical test of the treatments *L, H* or *P* vs *C* is performed. The preplanned testing strategy follows the closed test principle (Marcus et al 1976).

Definitions and abbreviations:

- Comparisons of treatment vs. control: $i = L, H, P$, where *L* denotes the comparison of the low dose vs. placebo control *C*, *H* the comparison of the high dose vs. placebo control and *P* the comparison of the pooled high and low dose vs. placebo control.
- Endpoints: $e = T, A$ where *T* is the time to diagnosis and *A* the composite endpoint APCC.

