- A single null hypothesis of no effect of treatment comparison *i* on endpoint *e* is denoted by H_e^i .

Intersection hypotheses are denoted by concatenating the index pairs e^i of each hypothesis,

for example, $H_{TTA}^{LHH} = H_T^L \cap H_T^H \cap H_A^H$.

An intersection hypothesis that reference both treatment arms for an endpoint e are abbreviated as $H_e^P = H_e^L \cap H_e^H$. Whenever such a pair occurs it will be collapsed to one hypothesis since the data will be pooled and a single test conducted, for example,

$$H_{T,T,A}^{L,H,H} = H_{T,A}^{P,H}$$

Thus, the 15 intersection hypotheses resulting from the 4 original elementary hypotheses on 2 doses and 2 endpoints can be rewritten with either one or two index pairs.

- P-values resulting from the 4 univariate tests across both stages are denoted as p_e^i for, $e = T, A; i = L, H$, while p-values for the 2 possible pooled tests on the 2 endpoints are denoted as $p_e^P, e = T, A$.

P-values resulting from tests on first and second stage data are accordingly denoted by $p_{e,j}^i, e = T, A; i = L, H; j = 1, 2$ and $p_{e,j}^P, e = T, A; j = 1, 2$.

- Pooling of doses refers to pooling of all participant data initially randomized to both the 50 mg and 15 mg once daily dose arms, irrespective of dose regimen changes during the course of the trial.

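### The protocol contradicts itself on who belongs to the primary active arm if the dose regimen modification (DRM) is activated

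*Protocol*

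**What the plan says.** **The lists.** Protocol Section 9 (Data analysis) describes the primary treatment arms for efficacy with and without a DRM. With a DRM, the primary active arm is made up of three groups:

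1. "those who received CNP520 50 mg once daily dose followed by CNP520 LDR", glossed as those first randomised to Arm #1 who later switch;
2. "those who received CNP520 15 mg once daily dose followed by CNP520 LDR", with the same gloss for Arm #2;
3. "those who received CNP520 LDR dose only (those who were randomized to active treatment arm after the DRM".

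Section 17.1 (Appendix 5) gives the same three groups under the lead-in "The primary active arm (pooled across all active arms) consists of the following participants".

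**Placebo.** Section 9 sets no switch condition: "The primary placebo arm (Arm #3) consists of all the participants who have been randomized to Arm #3 and received placebo regardless of DRM".

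**Text that includes everyone.**

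- Section 9.1 puts all efficacy analyses on the full analysis set (FAS), meaning everyone randomised who started study drug.
- Sections 3.2 and 9.4 define the primary active arm under a DRM by pooling the two active arms, with no further condition.
- Section 17.1, a little after its list, says: "Pooling of doses refers to pooling of all participant data initially randomized to both the 50 mg and 15 mg once daily dose arms". It adds that later changes of regimen make no difference.
- Section 9.4.4 removes data collected long after stopping drug only in supportive analyses.

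**The concern.** Someone randomised to 50 mg or 15 mg who permanently stopped, withdrew or died before the switch never received the LDR. That person is in none of the three listed groups. A placebo participant with the same history stays in. Taken at face value, the list therefore puts a condition on the active arm that depends on what happened after randomisation and has no counterpart on placebo.

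Membership of the primary comparison should not be open to two readings. A programmer working from the lists would build a different active arm from one working from Section 9.4 or the pooling definition, and both primary endpoints would be affected. Section 5.6.2 asks people who stop drug to keep attending visits, so the literal reading could discard outcomes that had been collected. Two other statements rest on the full randomised arms: Section 9.7 treats bias from the DRM as small enough to ignore, and Section 9.8 expects more power under a DRM because more participants enter the comparison.

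**Working it through.** **1. The plan's own figures reproduce.** Inputs from Section 9.8: hazard ratio (HR) 0.75, two-sided alpha 4%, 30% control events and 30% drop-out over 60 months, 2 years of accrual, 5 to 7 years of follow-up.

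- Events for 80% power at 1:1 (Schoenfeld): 4(2.054 + 0.842)² / (ln 0.75)² ≈ 406. Freedman's formula gives 411. The plan has 408, at which power is 80.3%.
- Expected events with exponential hazards: 229.5 placebo, 180.3 on 50 mg, 90.2 on 15 mg. The plan has 228, 180 and 90.
- Yearly drop-out: 1 − 0.7^(1/5) = 6.9%, as stated.
- All active participants pooled, 1200 vs 800, 498 events: 0.2877 × √(498 × 0.6 × 0.4) − 2.054 = 1.09, so power is 86%. This agrees with the statement that power rises under a DRM.

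The point disputes none of these numbers.

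**2. How many participants the list leaves out.** The documents give neither a rate of stopping drug nor a DRM date. Assumptions: the rate equals the planned drop-out, h = −ln(0.7)/5 = 0.0713 per year; accrual is uniform over 2 years; the DRM occurs at time d ≤ 2 years (Section 9.6 places its assessment in the recruitment period). Then

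number left out = 1200 × (d/2) × [1 − (1 − e^(−hd))/(hd)]

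- d = 1: 600 × 0.0348 = 20.9
- d = 2: 1200 × 0.0681 = 81.7, or 6.8% of 1200

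At 6 and 18 months the counts are 5 and 46. At 2 years, half or double the stopping rate gives 42 or 156. The corresponding placebo stoppers, about 14 at 1 year and 54 at 2 years, would all be kept.

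**3. What that does to the comparison when the drug has no effect.** Simulation under HR 1: 1200 vs 800, 2-year accrual, analysis at year 7, event and stopping hazards both h, log-rank test at two-sided 4%. A false claim of benefit then has nominal probability 2%. Active participants who stopped before the DRM are removed and placebo is left intact. Except in the last row, stoppers are followed off drug. Ranges span repeated runs. The hazard multipliers are assumptions.

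| Hazard after stopping | DRM | HR | False benefit |
|---|---|---|---|
| unchanged | 2 years | 1.00 | about 2% |
| ×1.5 | 2 years | 0.98 | 3.6% to 4.0% |
| ×2 | 1 year | 0.99 | 2.8% to 3.1% |
| ×2 | 2 years | 0.96 | 5.5% to 6.3% |
| ×2, stoppers censored on stopping | 2 years | 1.00 | about 2% |

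Keeping everyone gave HR 1.00 and about 2% throughout.

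**The case against.** The strongest reply is that the list describes exposure and was never meant as an exclusion rule. Section 5.2 says that all participants already assigned to an active arm will be moved to the LDR, and the three groups mirror that path. The list's own lead-in in Section 9 names the pooled Arm #1 and Arm #2 and keeps the 3:2 ratio. Nothing in the protocol states an intention to exclude people who stopped early. This stands as the likely intent. It does not remove the conflict, because the list purports to say who makes up the arm, appears twice, and sits beside a placebo definition with no such condition. The FAS rule says who is analysed; it does not say which listed group a person who stopped early belongs to.

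A reader might infer more than the text supports:

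- **That these participants are in fact dropped from the primary analysis.** Sections 3.2, 9.1, 9.4 and the pooling definition in 17.1 all include them.
- **That those left out did badly on the original doses, so the result must favour CNP520 and the 5% error rate fails.** The DRM may be triggered by external data on other BACE inhibitors alone (Section 3.1), participants may stop for any reason (Section 5.6.2), and the documents give no evidence that early stoppers have a higher event hazard.
- **That the intention-to-treat sentence in Section 9.4.4 settles the matter.** The sentence, "The primary efficacy analysis will be based on an intention-to-treat principle", stands under the item on cholinesterase inhibitors and concerns participants who start those drugs.

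The size is also open to challenge. The 6.9% is study drop-out, and people who leave the study cannot be followed off drug; with censoring on stopping the bias vanishes. A DRM at 2 years is the last moment of planned accrual, and so the extreme case.

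**Conclusion.** The point holds as an internal contradiction. The lists in Sections 9 and 17.1 omit active participants who stopped before the switch, and other current text includes them. Read literally, the omission would be one-sided and would depend on post-randomisation events.

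The literal reading would remove about 21 to 82 of 1200 active participants for a DRM at 1 to 2 years, on the assumption that the planned drop-out rate is the rate of stopping drug. Any bias towards CNP520 requires both that stopping is related to outcome and that stoppers are followed off drug. If the hazard doubles after stopping, false benefit is roughly 3% (DRM at 1 year) to 6% (DRM at 2 years) instead of 2%. With stopping unrelated to risk there is none.

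There is no practical effect on this trial's report. SAP Sections 2 and 4 cancel the planned primary analyses after early termination. The SAP describes the DRM (Section 1.1.3) without restating or correcting the list, and the rationale for Amendment 03 says that Section 9 is left unchanged, so the contradiction remains in the current protocol text.

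**What to change.** In Sections 9 and 17.1, define the primary active arm under a DRM as all FAS participants randomised to Arm #1 or Arm #2, analysed as randomised, whether or not they ever received the LDR. Keep the three groups only as a description of exposure, and add those who received 50 mg or 15 mg alone so that the description is complete. This makes the active definition match the placebo definition, Section 9.4 and the pooling rule. It costs a sentence in each of two places and needs no new data. Because the primary analyses are cancelled, its value now is a consistent record and wording that is safe to reuse in another protocol.
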